1.3. STUDY OBJECTIVES

1.3.1. Primary Objectives:

The following primary objectives were specifically chosen to address gaps in the currently available data informing BDQ benefits and risks:

- To describe the type of hospital or outpatient setting administering MDR-TB treatment
- To describe MDR-TB treatment delivery modalities, including treatment and management programs in place, administration of drug under closely monitored conditions, and consultation with experts in clinical management of MDR-TB and public health authorities such as national MDR-TB advisory groups within National TB Control Programs
- To describe the demographic and clinical characteristics of MDR-TB patients participating in the registry
- To describe MDR-TB treatment regimen utilization including dosages, duration, past treatment history, past medical history, concomitant medications used for conditions other than TB
- To measure adherence to WHO guidance in terms of selection of MDR-TB regimens and selection of patients for BDQ treatment

- To describe the indication for use of BDQ
- To measure extent to which patient informed consent is obtained for receipt of BDQ
- To describe BDQ and background drug susceptibility testing expressed as minimum inhibitory concentration (MIC) at baseline and for isolates from the last positive specimens
- To actively monitor adverse events using cohort event monitoring, including the monitoring for drug-drug interactions
- To actively monitor for mortality events using cohort event monitoring that includes collection of cause of death where available
- To estimate the relative risk of adverse events and mortality events by comparing event rates among BDQ-treated patients to respective event rates among patients not treated with BDQ, adjusting for potential imbalances in predictors of receiving BDQ for treatment, as well as predictors of mortality, assuming the availability of comparable populations
- To describe the following treatment outcomes separately for patients with MDR-TB and patients with non- MDR cases or MDR status not documented, as stipulated by the WHO revised definitions for resistant TB cases in 2013: cured, treatment completed, treatment failed, died, lost to follow-up, not evaluated, and treatment success
- To compare the treatment outcomes of cured, treatment completed, treatment failed, died, lost to follow-up, not evaluated, and treatment success between BDQ-treated patients and patients not treated with BDQ

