2.2. Study Design Rationale

The prospective observational comparative cohort design of the registry was chosen to specifically meet the study objectives. Prospective data collection not only facilitates characterization of clinics treating MDR-TB patients and how care is delivered, as well as patients being treated, but also facilitates active pharmacovigilance via real-time identification and reporting of adverse events, including deaths. By including MDR-TB patients as well as all patients treated with BDQ, the study is able to assess the indication for BDQ use, as well as how BDQ is used. By including patients treated with BDQ and MDR-TB patients not treated with BDQ, the study is able to provide an assessment of the relative risk of adverse events and deaths for BDQ relative to the observed risk among similar MDR-TB patients. The study design also provides for drug sensitivity testing over time for MDR-TB patients as well as the possibility of collecting samples for future drug sensitivity testing. The registry design was chosen due to the limited data on BDQ utilization and treatment outcomes (clinical and microbiologic) as well as the limited information on treatment outcomes for other MDR-TB treatments. Patients will be treated at a limited number of healthcare sites under the early adopter program (WHO pilot sites) which facilitates targeting healthcare providers who treat MDR-TB with educational material on the importance of enrolling patients in the registry.

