4. STATISTICAL METHODS

4.1. Sample Size and Study Precision

The three year enrollment period of the registry is estimated to result in an enrollment of 3000 to 5000 BDQ-treated patients.

A cohort of 3000 patients gives a 95% probability of identifying an adverse event with an incidence rate of 1:1000.

Based on the sample size estimates below, a registry of 1000 BDQ-exposed patients would have 95% power to detect a Relative Risk of 2 assuming $\alpha = 0.05$ and a 1:1 ratio of BDQ-exposed patients to unexposed patients for events that occur with a frequency of at least 3%.

Power and Sample Size for Adverse Events Occurring with a Frequency of at Least 3%							
Exposed	Relative Risk						
	1.5	2	3	4	5	7	10
0	0.049985	0.049985	0.049985	0.049985	0.049985	0.049985	0.049985
100	0.133214	0.252768	0.559428	0.828643	0.961157	0.999754	1.000000
200	0.190756	0.414883	0.844041	0.986772	0.999721	1.000000	1.000000
300	0.243884	0.552078	0.952777	0.999299	0.999999	1.000000	1.000000
400	0.294233	0.663681	0.987120	0.999970	1.000000	1.000000	1.000000
500	0.342210	0.751574	0.996745	0.999999	1.000000	1.000000	1.000000
600	0.387925	0.819043	0.999224	1.000000	1.000000	1.000000	1.000000
700	0.431400	0.869774	0.999824	1.000000	1.000000	1.000000	1.000000
800	0.472639	0.907271	0.999961	1.000000	1.000000	1.000000	1.000000
900	0.511649	0.934588	0.999992	1.000000	1.000000	1.000000	1.000000
1,000	0.548449	0.954244	0.999998	1.000000	1.000000	1.000000	1.000000

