4.4.2. Analysis of Study Objectives

4.4.2.1. Descriptive Analyses

This analysis will describe and summarize the prescribing and utilization of MDR-TB treatments, as well as patient treatment outcomes (clinical and microbiologic), and TB isolate susceptibility. MDR-TB treatment will be summarized by patient demographics and clinical characteristics (comorbidities and concomitant medications). In addition, the details of MDR-TB treatment will be described including indication of use, dose, frequency, duration of use, usage with TB background regimen, and susceptibility of concomitant TB treatment regimens. Patients treated with BDQ outside of the MDR-TB indication will be summarized by patient demographics and clinical characteristics including indications of use, frequency, duration of use, usage with TB background regimen, and susceptibility of concomitant TB treatment regimens. Additionally,

treatment outcomes will be described separately for MDR-TB cases and non MDR cases or MDR status not documented (WHO, 2013³⁰).

Proportions and 95% confidence intervals will be estimated separately for BDQ-treated patients and non-BDQ-treated patients for each study objective.

Additionally the following treatment outcomes will be estimated separately for patients with MDR-TB for BDQ-treated patients and non-BDQ-treated patients: cured, treatment completed, treatment failed, died, lost to follow-up, not evaluated, and treatment success.

Analyses of MDR-TB drug susceptibility will use the total number of MDR-TB patients included in the registry. Proportions will describe the number of subjects whose post-enrollment isolates exhibit at least 4-fold increase in BDQ MIC in comparison to baseline MIC, provided that the post-baseline MIC is >0.25 mg/mL based on phenotypic methods on solid or liquid media. Additional proportions will describe the number of patients with pre-XDR and XDR-TB.

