4.5. Evaluation of Appropriateness of Comparison Study

The evaluation of appropriateness of a comparison of BDQ-exposed patients with non-BDQ-treated MDR-TB patients will be based on the consistency of the clinical

experience of the 2 cohorts. This assessment will be conducted based on distribution of propensity scores for receipt of BDQ or other treatment regimens.

The evaluation of clinical experience will assess the patients' clinical and demographic characteristics in relation to receipt of BDQ and other MDR-TB regimens. Information will be captured on the patients' clinical and demographic characteristics that could be predictive of treatment appropriateness. This information will be incorporated into multivariate model to identify a group of patients with similar characteristics to the BDQ cohort but treated with other MDR-TB treatments. All patients will be assigned a propensity score ranging from 0 to 1 that represents the fitted probability of receiving BDQ. The scores from non-BDQ-treated patients will be plotted against those for BDQ-treated patients. Overlap in the cohorts based on sample size estimates of approximately 750 patients per treatment group in the propensity space must exist for a comparison of safety events between the two groups. An epidemiologist trained in propensity score estimation and matching methodology will make this assessment on the epidemiological validity of a comparison between the 2 treatment cohorts.

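### Drug-susceptibility proportions are taken over all MDR-TB patients, including those without paired BDQ MICs, in conflict with the by-treatment split; acquired resistance may be understated as testing coverage falls

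*Protocol*

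**What the plan says.** Section 4.4.2.1 of the protocol gives a denominator for the whole susceptibility analysis: "Analyses of MDR-TB drug susceptibility will use the total number of MDR-TB patients included in the registry". The Synopsis repeats it. The next sentence in 4.4.2.1 defines the resistance measure: "Proportions will describe the number of subjects whose post-enrollment isolates exhibit at least 4-fold increase in BDQ MIC in comparison to baseline MIC", with the further condition that the later MIC exceeds a threshold. Pre-XDR and XDR proportions follow under the same rule. Neither place limits the denominator to patients with the MICs or susceptibility results that the measure needs.

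Two paragraphs earlier, 4.4.2.1 says: "Proportions and 95% confidence intervals will be estimated separately for BDQ-treated patients and non-BDQ-treated patients for each study objective". MIC testing is one of those objectives. Section 1.3.1 lists: "To describe BDQ and background drug susceptibility testing expressed as minimum inhibitory concentration (MIC) at baseline and for isolates from the last positive specimens". The Synopsis carries the all-patients denominator without the sentence on the split.

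**The concern.** A rise from baseline can be seen only in a patient with a baseline BDQ MIC and at least one later MIC. Followed as written, the rule leaves everyone else in the denominator, where they are in effect counted as having no rise. The reported proportion then falls whenever fewer MICs are done, whatever happens to resistance. The same holds for pre-XDR and XDR in patients without second-line results.

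Gaps in testing are foreseeable. Section 2.1 says that the registry does not influence care, section 5 warns that essential data may not be collected routinely, and follow-up MICs come from the last positive specimen, so a patient with no later positive specimen yields none.

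The protocol also leaves it unclear whether the MIC-rise proportion is pooled over BDQ and non-BDQ patients or split. Emergence of resistance to BDQ is one of the reasons given for the registry in the Synopsis and section 1.2, so an estimate that looks reassuring because few patients were tested would mislead on a core aim.

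**Working it through.** The protocol gives no expected proportion, number of paired isolates or precision for this measure, so there is no figure to reproduce. The check is how far the stated denominator moves the result.

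**Inputs**
- BDQ-treated patients: section 4.1 expects "enrollment of 3000 to 5000 BDQ-treated patients"; 3000 is used.
- Non-BDQ patients: section 2.2 confirms that they are included, but no number is planned. Two illustrative sizes are used: 3000, from the "1:1 ratio of BDQ-exposed patients to unexposed patients" in the power statement of section 4.1, and 750, from the "approximately 750 patients per treatment group" in section 4.5. Neither is a recruitment target for this group.
- *e*, the share of BDQ-treated MDR-TB patients with paired MICs: not given; varied from 75% to 10%.
- Assumptions: all BDQ-treated patients counted are MDR-TB cases, and patients never given BDQ contribute no rises.

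**Formula.** Let *p* be the proportion among BDQ-treated patients with paired MICs and *b* the BDQ-treated share of the denominator. Reported proportion = *p* × *b* × *e*, so the reported figure is lower than *p* by the factor 1/(*b* × *e*).

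- Split by treatment: *b* = 1.
- Pooled, 3000 and 750: *b* = 3000/3750 = 0.8.
- Pooled, 3000 and 3000: *b* = 3000/6000 = 0.5.

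| *e* | Split | Pooled, 3000 + 750 | Pooled, 1:1 |
|---|---|---|---|
| 75% | 1.33 | 1.67 | 2.67 |
| 50% | 2.0 | 2.5 | 4.0 |
| 30% | 3.33 | 4.17 | 6.67 |
| 20% | 5.0 | 6.25 | 10.0 |
| 10% | 10.0 | 12.5 | 20.0 |

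Non-BDQ patients alone (*e* = 100%) give a factor of 1.25 or 2.0 when pooled, and 1.0 when split. Missing pairs alone give 1/*e*.

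**Example.** Assume 3000 BDQ and 3000 non-BDQ patients, *e* = 20% (600 with pairs) and 60 rises; the 20% and the 60 are illustrations. Wilson 95% intervals:
- BDQ-treated with paired MICs: 60/600 = 10.0% (7.8 to 12.7).
- All BDQ-treated: 60/3000 = 2.0% (1.6 to 2.6).
- All MDR-TB patients: 60/6000 = 1.0% (0.8 to 1.3).

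Interval width relative to the estimate is about 4.9/10.0 = 0.49, 1.0/2.0 = 0.50 and 0.5/1.0 = 0.50, so relative precision hardly changes.

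**Pre-XDR and XDR.** The same logic gives a factor of 1/*t*, with *t* the share with second-line results, if untested patients resemble tested ones. Section 1.1.1 quotes XDR at 13.7% of EU/EEA MDR-TB cases tested for second-line susceptibility. Purely as arithmetic, a registry with that proportion among tested patients and *t* = 50% would report 13.7% × 0.50 = 6.85%, which is not comparable with the background figure.

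**The case against.** The strongest case against has five parts.

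- **The split already applies.** The by-treatment sentence covers each objective, and MIC is a listed objective, so patients never given BDQ may not be in the divisor at all. This stands as far as it goes. A reader might infer from the denominator sentence that they are included, but the protocol says both things and does not settle it. Under the split, untested patients still remain.
- **The sentence may only define the population.** The registry takes BDQ users whatever the indication, so the wording could be meant to keep non-MDR cases out of the resistance analysis, with rules for missing results left to the separate statistical analysis plan. That intention is plausible. Still, the text speaks of the total number of MDR-TB patients, in two places, immediately before the proportions. It states a rule and does not merely leave a gap. The protocol does not say outright that untested patients are scored as negative; that is the consequence of following the rule.
- **The size is assumed.** This stands. A reader might take the dilution to be several-fold, or 7- to 20-fold as in the lower right of the table. Those values need a low paired share and a large pooled non-BDQ group, and the protocol gives neither. At 75% coverage with the split, the factor is 1.33.
- **A paired-only denominator is biased too.** This stands. Early converters may give no later positive isolate, so the paired group over-represents patients who stay or become culture-positive again, and overstates emergence among all treated patients.
- **The interval is not wrong.** This also stands. A reader might call it falsely narrow, but it is valid for the proportion it describes, and estimate and width shrink together. The problem is what the proportion means.

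It is also true that the measure is descriptive, with no test or decision rule attached.

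**Conclusion.** The concern holds in a limited form. The denominator in section 4.4.2.1 and the Synopsis includes patients who cannot show a four-fold rise because they lack paired MICs, and it is not reconciled with the by-treatment split in the same section. Relative to patients with paired MICs, the MIC-rise proportion is understated 1.3-fold at 75% coverage, 2-fold at 50% and 5-fold at 20% if the split governs, and by twice that if groups are pooled at an assumed 1:1. Coverage and the size of the non-BDQ group are assumptions, so no single factor can be claimed.

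Nor is the paired figure the true risk. If the risk in untested patients lies between zero and that in tested patients, the risk among all BDQ-treated patients lies between the all-treated and the paired proportions. That is why both are needed. The pre-XDR and XDR proportions have the same weakness for patients without second-line results.

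**What to change.** In section 4.4.2.1 and the Synopsis, replace the denominator sentence so that it states:

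- The MIC-rise analysis is split by BDQ treatment.
- For BDQ-treated MDR-TB patients, the report gives the number with a baseline and a post-baseline BDQ MIC, the proportion with a rise among them, and the same count over all BDQ-treated MDR-TB patients.
- Two notes accompany these figures: the paired group over-represents patients who stay or revert to culture-positive, and the all-treated figure counts untested patients as having no rise.
- Non-BDQ patients are reported separately.
- Pre-XDR and XDR proportions are based on patients with second-line susceptibility results, with the number tested shown.

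This changes analysis wording in two places and needs no new data or enrolment. The cost is that proportions among tested patients rest on fewer patients and have wider intervals: in the example, 7.8% to 12.7% on 600 patients against 0.8% to 1.3% on 6000.

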1. INTRODUCTION

1.1. Background

On December 28, 2012 the United States (U.S.) Food and Drug Administration (FDA) granted Janssen Therapeutics, Division of Janssen Products, LP accelerated approval to SIRTURO™ (bedaquiline) tablets for the treatment of pulmonary multi-drug resistant tuberculosis (MDR-TB) as part of combination therapy in adults. The European Commission granted conditional approval to SIRTURO™ in the European Union (EU) on March 6, 2014. Bedaquiline (BDQ) is also registered in the Russian Federation and South Korea, and is currently under review for approval in other countries worldwide.

BDQ has a novel mechanism of action (adenosine 5'-triphosphate [ATP] synthase inhibition), potent in vitro activity against both replicating and non-replicating bacilli, and significant bactericidal and sterilizing activity in the murine model of TB infection. It has been tested in vitro against multiple strains of *M. tuberculosis* and is equally active against drug susceptible (DS), MDR_{H&R} (resistant to isoniazid and rifampin only), pre-extensively drug resistant (XDR), and XDR strains of *M. tuberculosis* (Huitric 2007¹³, Lounis 2012¹⁹). Due to its novel mode of action, BDQ defines a new class of anti-TB compounds. It is a diarylquinoline which is the first new anti-tuberculosis drug since 1998 (rifapentine received accelerated approval in the US on 22 June 1998). The distinct target and mode of action of BDQ minimizes the potential for cross-resistance with existing anti-TB drugs.

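### The emergent-resistance rule sets its MIC floor in mg/mL (250 micrograms/mL), probably a 1000-fold unit slip that would idle the 4-fold criterion and push the reported proportion towards zero

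*Protocol*

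**What the plan says.** Section 4.4.2.1 defines the proportion by two conditions that must both hold. The first is relative: "post-enrollment isolates exhibit at least 4-fold increase in BDQ MIC in comparison to baseline MIC". The second is an absolute floor: "provided that the post-baseline MIC is >0.25 mg/mL based on phenotypic methods on solid or liquid media". The synopsis carries the same rule with the same number and unit.

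The denominator is set in the same paragraph: "Analyses of MDR-TB drug susceptibility will use the total number of MDR-TB patients included in the registry".

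The rule serves a stated aim. Section 1.2 names emergence of resistance among the things the registry is to evaluate, and a primary objective in section 1.3.1 is to describe susceptibility as "minimum inhibitory concentration (MIC) at baseline and for isolates from the last positive specimens".

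On the drug's activity, section 1.1 says only that it has "potent in vitro activity against both replicating and non-replicating bacilli". The protocol gives no BDQ MIC value, distribution, tested concentration range or breakpoint, and no source for the figure 0.25.

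**The concern.** A rule that joins a fold rise to an absolute floor normally lets the fold rise carry the definition. The floor removes rises that stay within low, still-susceptible concentrations. Printed in mg/mL, the floor lies so high that these roles are reversed: the fold rise hardly ever matters, and the floor alone decides who is counted. That sits badly with a drug described as potent.

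This is the only rule in the protocol for counting emergent BDQ resistance. If it were programmed literally and BDQ MICs are low, patients with a clear rise would not be counted. The shortfall would then be divided by all MDR-TB patients in the registry and reported with a 95% confidence interval, so a proportion near zero could look both low and precise. A reader would take it as evidence that resistance is not emerging.

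**Working it through.** The protocol does not derive the threshold, so there is no figure to reproduce. The check is a unit conversion, followed by asking which of the two conditions decides.

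**Inputs from the protocol (synopsis and 4.4.2.1)**
- Floor T: above 0.25 mg/mL.
- Relative criterion: at least 4-fold over the baseline MIC, b.

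**Input assumed, not in the protocol**
- Baseline MICs from 0.01 to 8 micrograms/mL. The range is deliberately wide because the protocol supplies no values.

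**Step 1, conversion.** 0.25 mg/mL × 1000 micrograms/mg = 250 micrograms/mL (250 mg/L).

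**Step 2, when the 4-fold criterion decides.** A patient is counted if the later MIC is at least 4b and also above T. The 4-fold criterion decides only when 4b > T, that is, b > T/4.
- As printed: 250/4 = 62.5 micrograms/mL. For every baseline up to 62.5 the floor alone decides.
- If the unit were micrograms/mL: 0.25/4 = 0.0625 micrograms/mL. The 4-fold criterion decides for every baseline above that.

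**Step 3, fold rise needed to be counted.** Required rise = max(4, T/b). Where T/b is the larger, the rise must exceed it.

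| Baseline MIC (micrograms/mL, assumed) | Rise needed, floor 250 micrograms/mL (as printed) | Rise needed, floor 0.25 micrograms/mL |
|---|---|---|
| 0.01 | 250/0.01 = 25,000-fold | 0.25/0.01 = 25-fold |
| 0.06 | 250/0.06 = 4,167-fold | 0.25/0.06 = 4.2-fold |
| 0.12 | 250/0.12 = 2,083-fold | 4-fold |
| 1 | 250/1 = 250-fold | 4-fold |
| 8 | 250/8 = 31-fold | 4-fold |

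Even at the top of the assumed range, the rise needed is about eight times the stated 4-fold (31.25/4 = 7.8). In two-fold dilution steps, a 4-fold rise is 2 steps. As printed, the rule needs about 5 steps at a baseline of 8 micrograms/mL and nearly 15 at 0.01.

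**Step 4, reading the two versions.** With the floor in micrograms/mL both conditions do some work across the assumed range: the floor decides at the lowest baselines and the 4-fold rise elsewhere. With the floor in mg/mL the 4-fold condition does none anywhere in that range. The structure of the rule therefore favours the smaller unit, but it does not prove it.

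**The case against.** Four counter-arguments deserve weight.

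1. **The unit may not be the sponsor's.** A micro sign can turn into an m when a PDF is converted to text. The agreement between the synopsis and 4.4.2.1 is not independent confirmation, because the two sentences are nearly identical and would be misread alike. Other symbols (the greater-than-or-equal sign, alpha) survive in the text, which lowers the risk without excluding it. This stands, and it makes the original PDF the first thing to check.

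2. **The protocol gives no MIC scale.** The two places do not contradict each other, and a qualitative statement of potency fixes no number. A reader might infer that the rule would count essentially nobody and return about 0% whatever the true rate. The documents do not support that: it needs BDQ MIC values that they do not contain. What can be said is conditional on the assumed range.

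3. **The consequence is limited.** MICs are themselves to be described (1.3.1, 4.2.2 and, for baseline isolates, 4.4.1), so an implausible zero would sit beside data that could expose it, and the proportion can be recomputed from stored values. No sample size, power or alpha figure uses the threshold. This stands and lowers the severity.

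4. **Later documents may settle it.** The synopsis promises a separate analysis plan, and section 4.2 says definitions are still being worked out with the WHO. That makes literal programming less likely. It does not make the printed threshold sound, because the protocol is the text those documents will follow.

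**Conclusion.** The point holds in conditional form. As printed, the floor is 250 micrograms/mL, and the 4-fold criterion is idle for every baseline MIC up to 62.5 micrograms/mL. These two statements need no assumption beyond the printed unit. Together with the description of the drug as potent in vitro, they point to a unit slip of a factor of 1000.

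The effect on the result rests on an assumption. With baseline MICs of 0.01 to 8 micrograms/mL, being counted would take a rise of more than 25,000-fold down to about 31-fold, instead of the stated 4-fold. The reported proportion would then be biased towards zero. How far cannot be derived from the protocol.

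Two further inferences go too far: that the sponsor has certainly made an error, since the PDF conversion is not excluded, and that the intended value is certainly 0.25 micrograms/mL, since no passage states it.

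Severity is moderate. The proportion is descriptive but serves a stated aim of the registry, and a wrong value would err in the reassuring direction.

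**What to change.** 1. Check the unit in the original PDF, in both the synopsis and 4.4.2.1. If it reads micrograms/mL there, nothing further is needed.
2. If mg/mL is confirmed as printed, compare the threshold with the concentration range the testing laboratory uses on solid and on liquid media.
3. Correct the unit in both places together, presumably to micrograms/mL, and do so before the proportion is programmed.
4. Keep each stored MIC with its unit, so that the count can be recomputed if needed.

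The cost is one query to the laboratory and two small text edits. Sample size, data collection and the other analyses are unaffected.

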An increasing number of TB cases that are resistant to isoniazid and rifampicin plus a fluoroquinolone and at least one injectable second-line drug, known as extensively drug-resistant TB or XDR-TB, have been reported. XDR-TB has been documented in 92 countries globally. Surveillance data from 79 countries and territories revealed the average proportion of MDR-TB cases with XDR-TB was 9.6% (95% CI: 8.1% to 11%) (WHO 2013²⁷). In the EU/EEA Region, the prevalence of XDR among MDR-TB cases tested for second-line drug susceptibility was 13.7% (range 0 to 50%) in 2012 (ECDC 2014⁹).

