1.2. Overall Rationale for the Study

A post marketing requirement relative to the accelerated approval of bedaquiline by the U.S. FDA included the development of a patient registry for BDQ-treated patients. Additionally, the WHO issued interim policy guidance on the use of BDQ in the treatment of MDR-TB identified the need for collection of additional data to further evaluate the benefits and risks of BDQ treatment beyond data provided from the BDQ Phase II clinical development program. Specifically, the interim guidance identified the need to collect additional data from larger patient populations representative of the target population for BDQ treatment that would be able to yield results with high precision and generalizability to global populations with respect to efficacy, safety, and emergence of resistance to BDQ or to drugs in background regimen.

Janssen Research and Development LLC proposes the establishment of a prospective, multi-country MDR-TB registry to further assess the benefits and risks of BDQ by evaluating BDQ safety, effectiveness, and emergence of resistance, BDQ drug utilization, and adherence to WHO guidance on the use of BDQ in MDR-TB treatment.

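### Pre-XDR/XDR-TB is planned as an untimed proportion of all MDR-TB patients, so as written it does not estimate acquired resistance to background drugs

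*Protocol*

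**What the plan says.** Section 1.2 of the protocol (and the Synopsis) gives the reason for the registry: larger populations are needed to inform "efficacy, safety, and emergence of resistance to BDQ or to drugs in background regimen". The registry's own aim repeats the theme: "evaluating BDQ safety, effectiveness, and emergence of resistance, BDQ drug utilization".

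Section 1.3.1 makes susceptibility to BDQ and to background drugs a primary objective, measured as "minimum inhibitory concentration (MIC) at baseline and for isolates from the last positive specimens".

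Section 4.4.2.1, repeated in the Synopsis, then sets the analysis in three steps:

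- Denominator: "Analyses of MDR-TB drug susceptibility will use the total number of MDR-TB patients included in the registry".
- BDQ: the proportion of patients whose "post-enrollment isolates exhibit at least 4-fold increase in BDQ MIC in comparison to baseline MIC", subject to a minimum post-baseline MIC.
- Background drugs: "Additional proportions will describe the number of patients with pre-XDR and XDR-TB".

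The same section asks for proportions and 95% confidence intervals separately for BDQ-treated and non-BDQ-treated patients, for each objective.

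**The concern.** The two halves of the resistance aim are handled differently. For BDQ, the measure is a within-patient change from baseline. For background drugs it is a head count with no time point and no reference to baseline.

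Two things follow if the text is applied as it stands. First, prevalent and acquired resistance fall into one number, and the prevalent part is likely to dominate it. Second, patients already XDR at entry, who cannot newly become XDR, stay in the denominator, as do patients with no later isolate.

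What is at stake is whether the registry delivers an estimate of emerging background-drug resistance, one of the reasons given for setting it up. Because results are shown by cohort, a reader may also take a difference in baseline resistance for a difference in resistance arising on treatment.

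**Working it through.** The protocol gives no target, rate or precision for pre-XDR/XDR or for acquired resistance, so there is no planned figure to reproduce. The check below shows how the measure behaves, using XDR as the example.

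**Inputs**
- Baseline XDR share among MDR-TB, b: 9.6% (global) and 13.7% (EU/EEA), both from section 1.1.1.
- BDQ-treated patients: about 3000 (section 2.1).
- Acquisition risk among patients not XDR at baseline, a: not in the protocol. Assumed 1% to 5% in step 1, and 2%, 5% and 10% in step 2.
- BDQ-cohort baseline in step 2: assumed 9.6% to 40%.

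**Step 1: how much of the reported figure is baseline resistance**

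Reported proportion = b + (1 − b) × a. Baseline share = b divided by that proportion.

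- If these XDR shares applied to the BDQ cohort, the number XDR at entry would be 0.096 × 3000 = 288, or 0.137 × 3000 = 411.
- b = 9.6%, a = 1%: 9.6% + 90.4% × 1% = 10.5%; share 9.6/10.5 = 91%.
- b = 9.6%, a = 5%: 9.6% + 90.4% × 5% = 14.1%; share 9.6/14.1 = 68%.

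This step needs no imbalance between cohorts.

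**Step 2: what a baseline difference does to the cohort comparison**

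Use the same a in both cohorts, so the true relative risk (RR) of acquisition is 1.00, and a comparator baseline of 9.6%. For a = 5%, the comparator's reported proportion is 14.1%. The table gives the RR of the reported proportion, BDQ versus non-BDQ.

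| BDQ baseline | a = 2% | a = 5% | a = 10% |
|---|---|---|---|
| 9.6% | 1.00 | 1.00 | 1.00 |
| 13.7% | 1.35 | 1.28 | 1.20 |
| 20% | 1.89 | 1.70 | 1.50 |
| 30% | 2.75 | 2.37 | 1.98 |
| 40% | 3.61 | 3.05 | 2.47 |

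For example, with a BDQ baseline of 20% and a = 5%: 20% + 80% × 5% = 24.0%, and 24.0/14.1 = 1.70.

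**Step 3: acquired cases over the stated denominator**

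If acquired cases were counted but divided by all MDR-TB patients, the RR becomes (1 − b in BDQ)/(1 − b in comparator), whatever a is. At 20% this is 0.80/0.904 = 0.88; at 30% it is 0.70/0.904 = 0.77. The distortion now runs the other way, so both the numerator and the denominator need changing.

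**Step 4: does another section supply the estimate?**
- Section 4.4.1 describes baseline susceptibility for the cohort, which gives no within-patient change.
- Section 4.2.2 includes acquired resistance to fluoroquinolones or injectables, but only as one criterion of Treatment Failed, and only where treatment ended or at least two drugs were permanently changed because of it.
- Section 4.2.3 lists pre-XDR/XDR as a potential confounder. The model adjustment in section 4.4.2.2 concerns adverse events and death, not this proportion.

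None of these yields acquired background-drug resistance as a measure of its own.

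**The case against.** The strongest reply is that this is one loosely worded sentence in a protocol that announces a separate statistical analysis plan, where time points and denominators of descriptive proportions are usually settled. The sentence is silent on timing and does not say that baseline and acquired cases are to be pooled. That much is fair. However, the protocol itself fixes the denominator, and it defines emergence for BDQ in the preceding sentence but not for background drugs. A plan that follows the text literally would carry the gap forward.

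Three stronger readings are tempting, and the document does not support them.

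- A reader might infer that emergence of background-drug resistance cannot be measured at all. It can: section 1.3.1 plans background-drug MIC at baseline and at the last positive specimen, and section 2.2 provides for susceptibility testing over time. The shortfall is in the stated measure, not in the planned data.
- A reader might infer that everything is reported as one pooled proportion. Section 4.4.2.1 speaks of proportions and reports by cohort.
- A reader might infer that BDQ will look worse through selection. The indication (no effective regimen otherwise available) and the channelling acknowledged in section 5 make this possible. But both comparator options in section 2.1 are patients eligible for BDQ, neither option is settled, and no between-group test of pre-XDR/XDR is planned. The protocol states no baseline difference, and step 2 shows no distortion without one. Equally, a difference is not ruled out, since section 3.1.1 admits all newly diagnosed MDR-TB patients.

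A further objection concerns the remedy. Patients who convert yield no later isolate to test, so a measure limited to paired isolates selects non-converters, and this selection could differ by cohort. This stands, and the fix has to allow for it.

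**Conclusion.** The point holds in limited form. As written, the pre-XDR/XDR measure does not separate baseline from acquired resistance and therefore does not estimate "emergence of resistance to BDQ or to drugs in background regimen" for the background-drug half of that aim. Under the protocol's 9.6% XDR share and an assumed 1% to 5% acquisition, roughly two thirds to nine tenths of the reported figure would be resistance present at entry.

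A between-cohort distortion is conditional. With equal true acquisition of 5% and a comparator baseline of 9.6%, the reported RR would be 1.70 or 2.37 if the BDQ baseline were 20% or 30%, and 1.00 if the baselines were equal. The acquisition risks and the BDQ baselines are assumptions. The change is worth making because it is small and uses data already planned.

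**What to change.** In the Synopsis and section 4.4.2.1, replace the pre-XDR/XDR sentence with two measures, each shown by cohort:

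- (a) the proportion with pre-XDR and with XDR-TB at baseline;
- (b) newly acquired pre-XDR or XDR-TB: patients below that resistance class at baseline who reach it on a later isolate.

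Give (b) over two denominators: all patients below the class at baseline who have a baseline result, and the subset who also have a post-baseline result. State how many patients have paired results in each cohort. Say that (b) is descriptive, because patients who convert provide no later isolate.

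The cost is a few sentences of text and no new data collection. The price in the results is smaller denominators, wider confidence intervals, and selection of non-converters in the paired subset. Showing both denominators makes that selection visible but does not remove it.
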